**Table 3 ARIA-E Parameters for Gantenerumab**

I BS	ET 50 (day)	γ	E max	EC 50 (μg/mL)
8.7E-6 (non-carrier) F 3.55E-5 (carrier) F	323.44 F	2.15 F	6.05±2.33	8.60±7.13

amyloid-related imaging abnormality–edema/effusion; F=fixed.

[figure not shown]
On inspection of the aducanumab PRIME study data (Sevigny et al. 2015), it became clear that the PK properties of gantenerumab and aducanumab are very similar. This supported an opportunity to test the hazard PK-PD model applied to gantenerumab on IV aducanumab ARIA-E data. The ARIA–E model, which already provides a good description of the gantenerumab ARIA-E data in Study WN25203 after 1 and 2 years of treatment, respectively, also predicted the aducanumab Phase Ib ARIA-E data with a great degree of accuracy (see [Figure 1](#)), including the ARIA rate differences across APOE ε4 allele groups (see [Figure 2](#)), even though this approach is limited based on external aggregated data. This finding indicated that doses much larger than those given in Study WN25203 can be described by the hazard model, provided that a constant dose regimen is used.

**Figure 1 ARIA-E Prediction for IV Aducanumab Using Bapineuzumab Hazard Model Adapted to SC Gantenerumab**

ARIA = amyloid-related imaging abnormality; ARIA-E = amyloid-related imaging abnormality–edema/effusion; IV = intravenous; SC = subcutaneous; SD = standard deviation.

**Figure 2 Model-Based Predictions of ARIA-E Occurrence for Aducanumab by APOE  $\epsilon 4$  Carrier and Non-Carrier Status and Dose for a Q4W Dosing Regimen: Comparison to Observed Data in the PRIME Study**

APOE  $\epsilon 4$ = apolipoprotein E, allele  $\epsilon 4$ ; ARIA=amyloid-related imaging abnormality; ARIA-E=amyloid-related imaging abnormality–edema/effusion; IV=intravenous; Q4W=every 4 weeks; SC=subcutaneous.

### 3. ARIA EVENTS UNDER DOSE TITRATION REGIMENS

#### 3.1 MODELING DATABASE AS OF 6 DECEMBER 2016

To check the validity of the model under titration conditions, two patient groups were selected from the open-label extension studies of WN25203 and WN28745. The first group comprised 71 patients who received increasing doses of gantenerumab and received placebo during the double-blind phase of the study. The second group comprised 417 patients who received a constant dose of gantenerumab and who did not have treatment-free intervals of more than 70 days. The first group is representative for the intended Phase III design, and the second group was included to enhance the database and link the model to previously established results (see [Table 4](#)).

## Appendix 5 Amyloid-Related Imaging Abnormality Hazard Model (cont.)

**Table 4 Patient Population Included in ARIA-E Model Building  
(Database as of 6 December 2016)**

Number of Patients (Number of Events)	Study WN25203	Study WN28745	Total	Comment
Total included in study	797 (63)	371 (35)	1168 (108)	
Placebo treatment	236 (2)	111 (3)	347 (5)	Excluded from model building
Total included in study on active drug	561 (61)	260 (32)	821 (103)	
Total on active drug before OLE, or treatment gaps >70 days	125 (11)	108 (23)	333 (44)	Excluded from model building
Total included in model building	436 (50)	52 (9)	488 (59)	
Titrated without prior treatment	19 (1)	52 (9)	71 (10)	Included in model building
Constant dosing, and treatment gaps <70 days	417 (49)	—	417 (49)	Included in model building

ARIA-E = amyloid-related imaging abnormality–edema/effusion; OLE = open-label extension.

As noted previously, the maximum likelihood estimation was performed using NONMEM software. Estimated model parameters were  $E_{max}$ ,  $EC_{50}$  and the baseline risk for carriers and non-carriers. ARIA-E events were observation interval censored.

Parameter estimates are shown in [Table 5](#).

[figure not shown]
**Table 5 ARIA-E Parameters for Gantenerumab When Applied to Titration Data**

$I_{BS}$	$ET_{50}$ (day)	$\gamma$	$E_{max}$	$EC_{50}$ ( $\mu\text{g/mL}$ )
$5.84 \pm 4.22 \text{ E-6}$ (non-carrier)	323.44 F	2.15 F	$7.12 \pm 1.03$	$5.16 \pm 2.85$
$11.9 \pm 7.30 \text{ E-6}$ (carrier)				

ARIA-E = amyloid-related imaging abnormality–edema/effusion; F = fixed.

Visual predictive checks were performed to assess model performance. As shown in [Figure 3](#), the overall model performance was acceptable. [Figure 4](#) presents a condition that was excluded from the model building. The apparent bias in the prediction might be attributable to a SCarlet RoAD study effect, which will be followed up during ongoing completion of the database.

[figure not shown]
Figure 3 Visual Predictive Check on Database Used for Model Building

ARIA-E = amyloid-related imaging abnormality–edema/effusion.

Notes: Kaplan-Meier curves of the data are shown in green (dashed lines: 90% CI). Simulated study data (100 replicated Kaplan-Meier curves) are shown in blue with their mean and 90% CI. Inserted are the number of model-predicted ARIA-E events at given percentiles (2.5%, 50% [median], and 97.5%) and the actual observed number of events.

**Figure 4 Visual Predictive Checks: Patients in SCarlet RoAD Study with Treatment Interruption >70 Days from Time 0 at Start of Open-Label Extension WN25203**

ARIA-E = amyloid-related imaging abnormality–edema/effusion; OLE = open-label extension.  
 Notes: Kaplan-Meier curves of the data are shown in green (dashed lines: 90% CI). Simulated study data (100 replicated Kaplan-Meier curves) are shown in blue with their mean and 90% CI. Inserted are the number of model-predicted ARIA-E events at given percentiles (2.5%, 50% [median], and 97.5%) and the actual observed number of events.

### 3.2 MODELING DATABASE AS OF 3 MARCH 2017

Table 6 presents an updated ARIA-E model building using data based on the cutoff date of 3 March 2017. In Table 7, ARIA-E parameters for gantenerumab are summarized when applied to titration data.

Appendix 5: Amyloid-Related Imaging Abnormality Hazard Model (cont.)

**Table 6 Patient Population Included in ARIA-E Model Building (Database as of 3 March 2017)**

Number of Patients (Number of Events)	Study WN25203	Study WN28745	Total	Comment
Total included in study	797 (69)	371 (60)	1168 (129)	
Placebo treatment	234 (2)	108 (3)	342 (5)	Excluded from model building
Database cleaning ongoing	3 (0)	—	3 (0)	Excluded from model building
Total included in study on active drug	560 (67)	263 (57)	823 (124)	
Long-term constant dose before titration	64 (9)	83 (17)	147 (26)	Excluded from model building
Total included into model building	496 (58)	180 (40)	676 (98)	
Titrated without prior treatment	24 (2)	67 [18]	91 (20)	Included in model building
Doses always smaller or equal to 225 mg	472 (56)	113 (22)	585 (78)	Included in model building

ARIA-E = amyloid-related imaging abnormality–edema/effusion.

[figure not shown]
**Table 7 ARIA-E Parameters for Gantenerumab when Applied to Titration Data**

$I_{BS}$	$ET_{50}$ (day)	$\gamma$	$E_{max}$	$EC_{50}$ ( $\mu\text{g/mL}$ )
$2.36 \pm 1.01 \text{ E-5}$ (non-carrier)	323.44 F	2.15 F	$6.07 \pm 0.702$	$7.75 \pm 2.70$
$3.75 \pm 1.30 \text{ E-5}$ (carrier)				

ARIA-E = amyloid-related imaging abnormality–edema/effusion; F = fixed.

Figures 5–7 show visual predictive checks for the final model. For both patients groups selected for model building, the diagnostics look acceptable (see Figures 5 and 6). For the excluded patient group who exhibited constant gantenerumab dosing followed by titration, often with 1 to 2 years of treatment gap in between, the diagnostics indicate a considerable mismatch. This could not be corrected by introducing covariates (such maximum treatment gap) into the model. It appears that the hazard model with its time component is not flexible enough for such regimens.

**Figure 5 Visual Predictive Check on Titration Data Used for Model Building**

[figure not shown]

ARIA-E=amyloid-related imaging abnormality–edema/effusion.

Notes: Kaplan-Meier curves of the data are shown in green (dashed lines: 90% CI). Simulated study data (100 replicated Kaplan-Meier curves) are shown in blue with their mean and 90% CI. Inserted are the number of model-predicted ARIA-E events (2.5%, 50% [median], and 97.5% percentiles), and the actual observed number of events. The apparent mismatch over the first 12 weeks is because no scan was performed during this period. Survival refers to the ARIA-E event-free proportion.

Appendix 5: Amyloid-Related Imaging Abnormality Hazard Model (cont.)

[figure not shown]
**Figure 6 Visual Predictive Check on Data Used for Model Building (Based on Data from Patients Enrolled in the Double-Blind WN25203 and WN28745 Studies and Dosed with 225 mg)**

ARIA-E = amyloid-related imaging abnormality–edema/effusion.

Notes: Kaplan-Meier curves of the data are shown in green (dashed lines: 90% CI). Simulated study data (100 replicated Kaplan-Meier curves) are shown in blue with their mean and 90% CI. Inserted are the number of model-predicted ARIA-E events at given percentiles (2.5%, 50% (median), and 97.5%) and the actual observed number of events. Survival refers to the ARIA-E event-free proportion.

**Figure 7 Visual Predictive Check on Excluded Data from Model Building**

ARIA-E = amyloid-related imaging abnormality–edema/effusion.

Notes: Kaplan-Meier curves of the data are shown in green (dashed lines: 90% CI). Simulated study data (100 replicated Kaplan-Meier curves) are shown in blue with their mean and 90% CI. Inserted are the number of model-predicted ARIA-E events at given percentiles (2.5%, 50% (median), and 97.5%) and the actual observed number of events. Survival refers to the ARIA-E event-free proportion.

### 3.3. MODELING DATABASE AS OF 8 JULY 2017

Table 8 presents an updated ARIA-E model building using data based on the cutoff date of 8 July 2017. In Table 9, ARIA-E parameters for gantenerumab are summarized when applied to titration data.

**Appendix 5: Amyloid-Related Imaging Abnormality Hazard Model (cont.)**

**Table 8 Patient Population Included in ARIA-E Model Building (Database as of 7 July 2017)**

Number of Patients (Number of Events)	Study WN25203	Study WN28745	Total	Comment
Total included in study	797 (75)	371 (60)	1168 (135)	
Placebo treatment	227 (2)	108 (3)	335 (5)	Excluded from model building
Database cleaning ongoing	2 (0)	—	2 (0)	Excluded from model building
Total included in study on active drug	568 (73)	263 (57)	831 (130)	
Long-term constant dose before titration	66 (14)	80 (16)	146 (30)	Excluded from model building
Total included into model building	502 (59)	183 (41)	685 (100)	
Titrated without prior treatment	36 (3)	70 (19)	106 (22)	Included in model building
Doses always smaller or equal to 225 mg	466 (56)	113 (22)	579 (78)	Included in model building

ARIA-E = amyloid-related imaging abnormality–edema/effusion.

**Table 9 ARIA-E Parameters for Gantenerumab when Applied to Titration Data**

[figure not shown]
$I_{BS}$	$ET_{50}$ (day)	$\gamma$	$E_{max}$	$EC_{50}$ ( $\mu\text{g/mL}$ )
$2.14 \pm 0.9742 \text{ E-5}$ (non-carrier)	323.44 F	2.15 F	$5.92 \pm 0.688$	$6.78 \pm 2.88$
$3.52 \pm 1.24 \text{ E-5}$ (carrier)				

ARIA-E = amyloid-related imaging abnormality–edema/effusion; F = fixed.

Figures 8–10 show visual predictive checks for the final model. For both patients groups selected for model building, the diagnostics look acceptable (see Figures 8 and 9). For the excluded patient group who exhibited constant gantenerumab dosing followed by titration, often with 1 to 2 years of treatment gap in between, the diagnostics indicate a considerable mismatch. This could not be corrected by introducing covariates (such maximum treatment gap) into the model. It appears that the hazard model with its time component is not flexible enough for such regimens.

[figure not shown]
**Figure 8 Visual Predictive Check on Titration Data Used for Model Building**

ARIA-E = amyloid-related imaging abnormality–edema/effusion.

Notes: Kaplan-Meier curves of the data are shown in green (dashed lines: 90% CI). Simulated study data (100 replicated Kaplan-Meier curves) are shown in blue with their mean and 90% CI. Inserted are the number of model-predicted ARIA-E events (2.5%, 50% [median], and 97.5% percentiles), and the actual observed number of events. Survival refers to the ARIA-E event-free proportion.

[figure not shown]
**Figure 9 Visual Predictive Check on Data Used for Model Building**

ARIA-E = amyloid-related imaging abnormality–edema/effusion.

Notes: Kaplan-Meier curves of the data are shown in green (dashed lines: 90% CI). Simulated study data (100 replicated Kaplan-Meier curves) are shown in blue with their mean and 90% CI. Inserted are the number of model-predicted ARIA-E events at given percentiles (2.5%, 50% (median), and 97.5%) and the actual observed number of events. Survival refers to the ARIA-E event-free proportion.

Figure 10 Visual Predictive Check on Excluded Data from Model Building

ARIA-E = amyloid-related imaging abnormality–edema/effusion.

Notes: Kaplan-Meier curves of the data are shown in green (dashed lines: 90% CI). Simulated study data (100 replicated Kaplan-Meier curves) are shown in blue with their mean and 90% CI. Inserted are the number of model-predicted ARIA-E events at given percentiles (2.5%, 50% (median), and 97.5%) and the actual observed number of events. Survival refers to the ARIA-E event-free proportion.

## Appendix 6 Management Rules for Amyloid-Related Imaging Abnormalities

Event	Characteristics	Action to Be Taken
ARIA-E	Asymptomatic ARIA-E and BGTS <4	
 
• Continue study drug at the same dose level (i.e., do not uptitrate) and repeat MRI scan 4 weeks later.               
 
– As long as BGTS is <4 and <math>\geq 1</math>, continue study drug at the same dose level and repeat MRI 4 weeks later.
 
– Once ARIA resolves, resume uptitration and obtain an MRI scan per the titration schedule. For participants randomized to the Q2W regimen, perform another MRI scan 3 months after ARIA resolution.
 
 
 

	Symptomatic ARIA-E (of any size) or asymptomatic ARIA-E and BGTS $\geq 4$	
 
• Temporarily interrupt study drug and perform MRI scans at 4-week intervals until symptoms and ARIA-E resolve.
 
• When symptoms and ARIA-E resolve, reintroduce study drug at dose given at the time the event was detected.               
 
– Perform an MRI scan before next scheduled dose for participants randomized to the Q4W regimen or after the second dose for participant randomized to the Q2W regimen.
 
– If no new ARIA-E is detected, resume uptitration and obtain an MRI per titration schedule. For participants randomized to the Q2W regimen, perform another MRI scan 3 months after study drug reintroduction.
 
 
 

	Any recurrence of ARIA-E	
 
• Treat the same as the first event (based on symptoms and BGTS).
 

ARIA-H	>15 ARIA-H cumulatively (should not include any disseminated LH)	
 
• Discontinue study drug.
 

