discontinuation will be implemented according to an ARIA-related dose-adjustment plan, described in Section 5.1.2. Safety findings (including unblinded individual patient and aggregate data) will be reviewed on a regular basis by the iDMC.

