All participants who prematurely discontinue treatment will continue participating in the study and will be asked to return for collection of safety and limited efficacy data (see Section 4.7.1).

[figure not shown]
Participants will undergo brain MRI examinations for safety monitoring and longitudinal changes in brain structure. MRI scans will be read by a central MRI reader (for more details regarding imaging-related criteria, see Section 4.1.2.2). Participants will also undergo standard tests to monitor safety (blood tests, ECG), as well as the Columbia–Suicide Severity Rating Scale (C-SSRS) to monitor for suicidality, tests for cognition, function, and QoL status. Blood samples for the assessment of PK samples, PD biomarkers, and ADA will be obtained from all participants.

The incidence and nature of adverse events, serious adverse events, ARIA-E, ARIA-H, ISRs, adverse events of special interest, ECGs, and laboratory abnormalities will be assessed on a regular basis by an unblinded iDMC.

An overview of the study design is provided in Figure 7. The schedule of activities is provided in Appendix 1.

Once the double-blind treatment period is completed, participants who consent and are eligible may opt to participate in an OLE. If the stand-alone open-label study (Study WN42171) is not open for enrollment at the time that a participant completes the double-blind treatment period of this study, then the participant will follow the OLE procedures described in this study (Section 4.3.2.2 and Appendix 1). These participants will then transition to Study WN42171 after they have completed the entire schedule of activities in the OLE of this study and the protocol for Study WN42171 is available and approved as per local requirements. If Study WN42171 is open for enrollment at the time that a participant completes the double-blind treatment period of this study, then the participant will enroll directly in Study WN42171 and not in the OLE portion of this protocol. *The OLE of Study WN39658 is not applicable in countries that cannot run Study WN42171.*

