**Figure 8 Overall Gantenerumab Dosing Design in the Double-Blind Treatment Period**

Q2W = every 2 weeks; Q4W = every 4 weeks; SC = subcutaneous.

For Q4W injections, a time window of  $\pm 7$  days is allowed for dosing visits. For Q4W injections, the recommended minimum time between doses is 3 weeks. The maximum recommended time between doses should not exceed 6 weeks. Once study drug is administered Q2W, the time window for dosing visits is  $\pm 3$  days. For Q2W injections, the recommendation is not to administer more than 1020 mg (i.e., 2 times 510 mg Q2W) within 28 days. Always return to the initial planned schedule per randomization for subsequent visits.

Regardless of dose, each participant will undergo up to a total of 49 dosing visits in scenario 1 or 55 dosing visits in scenario 2 (if applicable, see Section 3.3.1) in the double-blind treatment period of the study. Participants who have completed the double-blind treatment period at the time of the implementation of *the 12 week study extension*, will have undergone up to 43 dosing visits. Injections will be administered as one 0.8-mL (120-mg dose), one 1.7-mL (255-mg dose), or two 1.7-mL injections (510-mg dose) subcutaneously to the abdomen, respectively.

Placebo of identical composition (except protein) and identical volume to gantenerumab will be administered by SC injection to all participants randomized to placebo at the same frequency and using the same route of administration.

On study drug administration days that include efficacy assessments (see the schedule of activities in Appendix 1), study drug must be administered at the clinical site. Study

personnel preparing and administering study drug must not be involved with any efficacy assessments or safety evaluations.

At applicable sites, study drug may be administered by a trained nursing professional at the participant's home or another suitable location, if the participant has given written informed consent to participate in home nursing visits.

Rules for dosage modification and treatment interruption or discontinuation are provided in Section [5.1.2](#).

Any overdose or incorrect administration of study drug should be noted on the Study Drug Administration electronic Case Report Form (eCRF). Adverse events associated with an overdose or incorrect administration of study drug should be recorded on the Adverse Event eCRF.

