#### **4.6.5 Procedures for New MRI Findings**

In addition to any local reading according to local procedures and requirements, all MRI scans will be reviewed by an expert central reader within approximately 1 week of receipt and a report provided to the site. For the purposes of overall study relevant decisions and recommendations, including participant eligibility as well as for analysis, results from the expert central reader will be used. Any time the central reader identifies a new MRI finding the study center medical staff and the Sponsor will be rapidly notified (see Section [4.5.9](#)).

Refer to Section [5.1.2](#) for instructions in the event of new MRI findings (ARIA-E and ARIA-H).

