### **4.7 TREATMENT, PARTICIPANT, STUDY, AND SITE DISCONTINUATION**

#### **4.7.1 Study Treatment Discontinuation**

Participants must discontinue study treatment if they experience any of the following:

- Any medical condition that the investigator or Sponsor determines may jeopardize the participant's safety if he or she continues to receive study treatment
- Investigator or Sponsor determines it is in the best interest of the participant
- Pregnancy
- Upon evidence of more than 15 ARIA-H, cumulatively
- Any disseminated leptomeningeal hemosiderosis

All participants who withdraw from treatment will be asked to return 2 weeks after last dose in order to complete the early termination visit assessments.

In addition, participants who withdraw from treatment will be asked to return for collection of safety (except MRI) and limited efficacy data (i.e., the primary and secondary endpoints) at visits that have efficacy assessments according to the schedule of activities until the end of the double-blind treatment period, *and then the follow-up visits*, or until the last OLE follow-up visit (OLE Follow Up 2) for those who enrolled in the OLE.

The primary reason for study treatment discontinuation should be documented on the appropriate eCRF. Participants who discontinue study treatment prematurely will not be replaced.

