- In exceptional cases of 1) an ARIA-E that is asymptomatic with BGTS  $< 4$  and that is considered stable over consecutive MRI images by the Sponsor and investigator; or 2) symptomatic ARIA-E for which the imaging evidence of ARIA-E has resolved but

the CNS symptoms continue, the study drug can either be reintroduced or uptitrated, as applicable, and 4-weekly MRI monitoring may no longer be necessary, as determined by the Sponsor and investigator.

- Symptomatic ARIA-E is defined as onset or worsening of CNS symptom(s) that is/are temporally associated with ARIA-E MRI findings.
- Any recurrence of ARIA-E: Treat using the same procedures as for the first event (based on symptoms and BGTS).
- Participants who develop > 15 ARIA-H cumulatively will be discontinued from study drug (the cumulative number should not include any disseminated leptomeningeal hemosiderosis, i.e., up to 3 focal leptomeningeal hemosiderosis *either on the same scan or cumulatively*; a focal leptomeningeal hemosiderosis is counted as an ARIA-H).
- In cases where both ARIA-E and ARIA-H occur, the most conservative approach should be followed.
- A PK sample and a plasma biomarker sample will be obtained as soon as is practical (e.g., at an unscheduled visit) once the site becomes aware of the occurrence or worsening of ARIA-E or ARIA-H that meet the discontinuation criteria.
- The investigators may choose to perform additional MRI monitoring for ARIA at any time.
- MRI monitoring of ARIA findings should be conducted at approximately 4-week intervals.
- Any other new significant findings will be reviewed by the medical monitor and appropriate dose action will be taken.

The iDMC reviews the incidence of ARIA in an unblinded manner and may recommend adjustment of dosing regimen and/or ARIA management for the overall study population or for a specific *APOE* ε4 genotype.

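### Protocol 5.1.2 and Appendix 6 leave out the mandatory stop for disseminated leptomeningeal hemosiderosis set in 4.7.1, and they disagree on one follow-up MRI for mild ARIA-E

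*Protocol*

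**What the plan says.** **Stopping rules.** Protocol Section 4.7.1 opens its list with "Participants must discontinue study treatment if they experience any of the following". Two of its bullets concern ARIA-H: more than 15 cumulatively and, separately, "Any disseminated leptomeningeal hemosiderosis". Section 5.1.2 discontinues study drug for more than 15 cumulative ARIA-H and adds that "the cumulative number should not include any disseminated leptomeningeal hemosiderosis"; the parenthesis goes on to allow up to three focal areas, each counted as one ARIA-H. Appendix 6 has a single ARIA-H row, ">15 ARIA-H cumulatively (should not include any disseminated LH", with discontinuation as the action.

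**Where sites are sent.** Section 4.3.2.1 states "Rules for dosage modification and treatment interruption or discontinuation are provided" in 5.1.2. Section 4.6.5 refers to 5.1.2 "for instructions in the event of new MRI findings (ARIA-E and ARIA-H"; Section 4.5.9 also points there for MRI safety management. Section 5.1.1.1 names Appendix 6 as the source of the ARIA management rules. Section 1.3.3, which is rationale rather than a site instruction, likewise says that permanent "discontinuation will be implemented according to an ARIA-related dose-adjustment plan, described in Section 5.1.2". Neither 5.1.2 nor Appendix 6 cites 4.7.1. The one reference to 4.7.1 found in the text, in Section 3.1.1, concerns participants who stop treatment early being "asked to return for collection of safety and limited efficacy data (see Section 4.7.1".

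**Follow-up MRI.** For asymptomatic ARIA-E with BGTS at least 1 and below 4, Section 5.1.2 continues dosing at the same level with MRI every 4 weeks and, on resolution, goes back to the schedule of activities. For the same participants on Q2W dosing, Appendix 6 also requires a scan 3 months after ARIA resolution. For symptomatic ARIA-E, or BGTS of 4 or more, both texts require a scan 3 months after study drug is reintroduced.

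**The concern.** A site that receives a central MRI report of disseminated LH and turns to either ARIA text finds no instruction to stop, although 4.7.1 leaves no discretion. Other provisions depend on the same criterion without restating it: the bar on uptitration in 5.1.2, the extra PK and plasma samples for ARIA-H that meets discontinuation criteria, and the descriptive summary in SAP Section 5.6.3 of time to meeting the ARIA-H discontinuation criteria. Whether that is one criterion or two depends on which section is read.

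In the mild ARIA-E branch, a site following 5.1.2 alone would omit a safety scan that Appendix 6 makes mandatory for a participant who has been dosed throughout.

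At stake are participant safety and uniform conduct across about 175 centers. The efficacy inference is not.

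**Working it through.** **Part 1: the three texts side by side.**

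| Protocol text | More than 15 ARIA-H | Any disseminated LH |
|---|---|---|
| 4.7.1 | must stop | must stop |
| 5.1.2 | stop | only in a parenthesis about the count |
| Appendix 6 | stop | only in a parenthesis about the count |

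Take a participant with disseminated LH and 15 or fewer other ARIA-H. Under 4.7.1 the participant must stop. Under 5.1.2 the count rule is not met, and what remains is the general provision that the medical monitor reviews other significant findings and appropriate dose action follows. That is discretionary. Under Appendix 6 no row is met. The documents give no expected frequency of disseminated LH, so no number is put on this part.

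**Part 2: how late the next scan can be in the mild branch.**

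Inputs:
- Scheduled MRI in the Q2W phase (Protocol Appendix 1, Tables 2 and 3): Weeks 36, 48, 60, 76, 104 and 116.
- Q2W phase: Week 36 to Week 116, so 116 - 36 = 80 weeks.
- Assumption: 3 months is 12 to 13 weeks.

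Gaps between scheduled scans: 48 - 36 = 12; 60 - 48 = 12; 76 - 60 = 16; 104 - 76 = 28; 116 - 104 = 12 weeks.

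If ARIA-E resolves at Week r and the next scheduled scan is at Week S, the wait is S - r. It exceeds 3 months when r is before S - 12 (or S - 13). Only the 16- and 28-week gaps leave room for that:
- S = 76: r from Week 60 to 76 - 13 = 63 or 76 - 12 = 64, which is 3 to 4 weeks.
- S = 104: r from Week 76 to 104 - 13 = 91 or 104 - 12 = 92, which is 15 to 16 weeks.

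Total: 3 + 15 = 18 to 4 + 16 = 20 weeks. As a share of the Q2W phase, 18/80 = 22.5% to 20/80 = 25%.

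| Resolved at Week | Next scheduled scan | Wait (weeks) | Beyond 12-13 weeks |
|---|---|---|---|
| 60 | 76 | 16 | 3-4 |
| 76 | 104 | 28 | 15-16 |
| 80 | 104 | 24 | 11-12 |
| 84 | 104 | 20 | 7-8 |
| 88 | 104 | 16 | 3-4 |
| 92 | 104 | 12 | 0 |

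The Week 80 row is a natural case: ARIA-E found at the scheduled Week 76 scan and clear at the 4-week repeat.

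**The case against.** The strongest reply is that nothing is contradicted. Section 4.7.1 is the section on treatment discontinuation and it says must. Neither 5.1.2 nor Appendix 6 authorizes continued dosing after disseminated LH, so a site can comply with all three. The parenthesis may have been meant as none allowed, as similar wording in the imaging exclusion criterion (4.1.2.2) naturally reads. References in 5.1.2 and Appendix 6 to discontinuation criteria, in the plural, suggest that they assume rules stated elsewhere. Safeguards also exist: central reading with rapid notice to site and Sponsor (4.6.5), results before the next dose (4.5.9), and medical-monitor review. On the MRI, Appendix 6 already requires the scan, 5.1.2 lets investigators add scans at any time, and the branch is the mildest one, with no dose hold and no rechallenge.

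Much of this stands. It rules out a stronger conclusion that a reader might draw, that the protocol lacks a stop for disseminated LH or permits dosing after it. It also lowers the likelihood of harm. What it does not do is put the stop into the ARIA rules. In 5.1.2 the parenthesis is attached to the cumulative number, so it reads as a counting instruction. Medical-monitor review is not a mandatory stop. Permission to add a scan is weaker than the requirement in Appendix 6.

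**Conclusion.** The point holds as an inconsistency between sections of the operative safety rules. Two ARIA-H-related mandatory stops appear in 4.7.1 but only one in each of 5.1.2 and Appendix 6. One required follow-up scan appears in Appendix 6 but not in 5.1.2. Since 4.7.1 and Appendix 6 bind, both are omissions from particular texts and not absent requirements. They should be corrected because sites are directed to the texts that omit them.

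The MRI part is narrow. It concerns asymptomatic ARIA-E with BGTS at least 1 and below 4 on Q2W dosing. The first scheduled scan comes later than 3 months only for resolution in about Weeks 60-64 or 76-92, with a longest wait of 28 weeks. This assumes that 3 months is 12 to 13 weeks and that scans follow the 116-week schedule. The 22.5-25% is a share of calendar time and assumes Q2W dosing from Week 36. Participants whose uptitration is held start later.

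Two further inferences are not supported. A reader might think the two texts disagree on ARIA-E follow-up generally, but in the symptomatic or BGTS 4-or-more branch they agree on the 3-month scan. A reader might also size the problem from the predicted 26% ARIA-E rate in 508 gantenerumab participants, reduced using the BGTS medians of 7.0 and 9.0 in the earlier open-label extensions. That would count events during Q4W titration, to which the disputed scan does not apply. It would also ignore timing: both windows fall after the first year, when new ARIA-E had decreased substantially at the fixed doses of Study WN25203 (Protocol 1.2.3). The documents give no usable count for either part.

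There is no effect on the primary analysis, alpha or power.

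**What to change.** 1. In Protocol 5.1.2, add to the ARIA-H rule: *any disseminated LH: discontinue study drug*, and cite 4.7.1.
2. In Appendix 6, add a second ARIA-H row with the same trigger and action.
3. In 5.1.2, in the asymptomatic BGTS at least 1 and below 4 branch only, add: *Q2W participants: repeat MRI 3 months after ARIA-E has resolved.*
4. Leave the symptomatic or BGTS 4-or-more branch unchanged. Both texts already time that scan from reintroduction, and a second clock is not wanted.

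The cost is a few lines in 5.1.2 and one row in Appendix 6. No procedure is added beyond what 4.7.1 and Appendix 6 already require, and sample size, endpoints and analyses do not change.
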